Severe	
Easy: Single joint movements into the body (e.g., elbow flexion), mass finger flexion and cylindrical grasp
 
Matching Ability: Fluctuating between unable and partial ability to perform movements requiring movement of arm away from body (e.g., extend elbow, abduct shoulder, flex shoulder to 90 degrees). Partial ability to externally rotate shoulder, utilize palmar pinch.
 
Difficult: Unable to perform movements requiring simultaneous control of two joints (e.g., pronate/supinate forearm with elbow extended), or perform distal movements requiring precise muscle coordination.
	Reacquisition of partial ability to simultaneously flex the shoulder while extending the elbow

movements (stage 3) and onto recovery of distal isolated fine motor coordination (stage 6).⁴⁶ Fugl-Meyer applied a numeric rating scale to Brunnstrom's taxonomy thereby echoing her stages in the FMA-UE item order.³⁹

The progression of FMA-UE items reflected in the progression of UE impairment levels differ from the classic Brunnstrom stages in content and meaning. Rasch analysis of the FMA-UE challenged the assessment's construct validity and item-difficulty order (see **Preliminary Studies**).⁴⁴ The Rasch FMA-UE item-difficulty order provided a framework to interpret contemporary data providing evidence that arm movements are easier or more challenging based on the inherent task-specific computational demands of a movement task.⁵⁰

We argue that this Rasch FMA-UE measurement framework is a valuable foundation for designing treatment. We hypothesize that for each level of UE motor impairment, the Rasch FMA-UE classification system defines task-practice conditions that are the just-right balance between person-ability and task-difficulty and therefore provides a platform for designing patient-targeted therapy, investigating the specific effects of treatment and identifying responders/non-responders.

2e. The Rasch FMA-UE measurement framework as the basis for designing patient-targeted UE rehabilitation

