Table 3: Rasch FMA-UE Keyform Staging Chart

sequence of critical milestones marking post-stroke UE recovery; the ability to (1) simultaneously flex the shoulder and extend the elbow,⁴⁷ and (2) rotate the distal forearm while keeping the proximal joints still.⁴⁸ We identified FMA-UE items corresponding to the critical milestones then calculated Rasch-Andrich step thresholds⁴³ to mark boundaries between categories. Threshold values correspond to the vertical lines in the figure; the threshold marking the transition from severe to moderate = -0.12 logits, and from moderate to mild = 2.44 logits.

Item difficulty increases, the rating
e stair-steps to the right to illustrate
concept that more UE motor ability is
quired to accomplish more difficult
s. Three cut scores (vertical lines)
de the FMA-UE scale into 3
airment levels.

Cut-scores marking boundaries between UE impairment levels were based on an extensive literature review to identify a

This classification system defines UE motor behaviors characterizing each impairment level. Characteristic behaviors are illustrated by the expected FMA-UE item ratings for each stage's column in the figure. For example, people classified in the FMA-UE "severe" category are partially able to accomplish (grey shaded bars) elbow flexion, scapular elevation, shoulder adduction, mass finger flexion and more difficult movements such as

shoulder abduction, elbow extension, shoulder flexion, forearm pronation/supination. They will be unable to perform (blue shaded bars) all other items. Initial reacquisition of the ability to simultaneously flex the shoulder while extending the elbow (transition from scoring 0 to scoring 1 on the corresponding FMA-UE item) marks entry to the next category. People in the “moderate” category have near normal ability (expected score =2, green shaded bars) on items addressing elbow flexion, scapular elevation, finger flexion, relaxation of a tight fist. They should have partial ability (grey shaded bars) items addressing shoulder flexion to 90 degrees while keeping the elbow straight, external rotation, individual finger movements and some prehension skills. People in the “mild” category will exhibit “2” on the majority of items (green shaded bars) but may have partial ability (grey shaded bars) to perform the most difficult items such as wrist circumduction and hook grasp. The results of this analysis are also summarized in **Table 1**.

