3e. Kinematic and EMG findings to validate the Rasch-derived FMA-UE impairment categories

The purpose of this ongoing work is to validate the Rasch FMA-UE impairment categories with neuromechanical analyses. The 55 person sample enrolled in [name] CDA2 study was divided into subgroups according to the FMA-UE impairment category definitions described above. Extensive kinematic, EMG analyses were conducted while subjects performed 5 repetitions of an unrestrained reach-to-grasp task at a fast pace.

[figure not shown]

Figure 4: Angle-angle plots (red= stroke, blue = healthy)

utilizing approximately 20 degrees of shoulder flexion and virtually no elbow extension during the task. Person B (middle panel) with moderate impairment utilized approximately 40 degrees of shoulder flexion, and 20 degrees of elbow extension. Person C (right panel) with mild impairment utilized approximately 40 degrees of shoulder flexion and 45 degrees of elbow extension during the task. The performance of Person C, the mildly impaired individual is similar to the healthy individual whose data is presented in the rightmost panel. The healthy individual utilized approximately 70 degrees of shoulder flexion and 80 degrees of elbow extension to accomplish the task.

[figure not shown]

Figure 5: Elbow active range of motion

We tested the hypothesis that the groups formed by the Rasch FMA-UE impairment categories differed according to (1) elbow active range of motion (AROM), (2) hand path curvature (HPC), and (3) muscle onset. These neuromechanical variables were chosen because they measure critical aspects of motor control. Elbow active range of motion measures the ability to execute a goal directed movement, HPC is a surrogate measure of shoulder-elbow interjoint coordination, and muscle onset indicates the activation of key agonistic and synergistic muscles, thus indicates the integrity of descending motor tracts and motor neurons. Neuromechanical variables were averaged for the 5 trials, and compared with ANOVA and Tukey’s HSD post-hoc comparisons with significance defined as $p<0.05$.

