Inclusion criteria: 1) experienced ischemic stroke at least 3 mo. prior. The lesion type and location will be confirmed with medical records and past MRI or CT scan. This criteria is based on evidence suggesting lesions located in brainstem or cerebellum⁶⁴ and hemorrhagic⁶⁵ stroke may affect neural reorganization and observable patterns of UE motor recovery differently than lesion in the MCA distribution or ischemic etiology; 2) passive range of motion in affected shoulder, elbow and wrist within functional limits; 3) 20-90 years of age. Exclusion criteria: 1) pain in the affected UE that would interfere with movement; 2) unable to understand 3-step directions; 3) orthopedic condition or impaired corrected vision that would alter kinematics of reaching; 4) Any implanted ferromagnetic object that could be displaced by a magnetic field.⁶⁶; 5) a history of seizures. The study sample shall be inclusive of the general population of adults with stroke-related UE motor impairment without restriction in regard to gender, race, age, and socioeconomic status. Every effort will be made to include women, minorities and indigenous populations.

Procedure: Informed consent and all other procedures will occur in accordance with approval from the MUSC IRB and VAMC RR&D committee.

Study Flow: **Figure 9** illustrates the study flow.

[figure not shown]

Figure 9: Study Flow

evaluator. The 3 reflex items will not be administered because our previous work showed that these items do not contribute to measurement of the construct “voluntary” UE motor function. FMA-UE item ratings will be converted to a person-measure using Rasch analysis (Winsteps⁶⁸) with item-difficulty calibrations anchored to published values⁴⁴ which will assure stable person-measure estimates.

Procedure for Neuromechanical Evaluation: Kinematic and EMG analyses will be conducted at three time points (pre, mid and post).

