We have previously published our standardized procedures for neuromechanical evaluation.³² Subjects will be seated on a backless stool with the start posture standardized. Using their affected UE, subjects will perform 10 trials of reach-to-grasp (or touch) a soda can which will be placed at a location equal to 80% of arm’s length at midline, a location affording maximum shoulder flexion and elbow extension.⁵⁴ *No trunk constraint or arm support will occur during testing.* Kinematic data will be recorded with a 10-camera motion analysis system (PhaseSpace Inc) at a sampling frequency of 480 Hz using a marker set defined in our previous work.³² Kinematic data will be filtered with a 4th-order Butterworth low-pass filter (cutoff frequency of 12 Hz) then processed through a Visual 3D kinematic model using custom Matlab functions. Surface EMG electrodes will be applied to the center of the muscle bellies of the biceps (BI) and triceps (TRI) according to SENIAM procedures. The muscles are chosen because of their important roles as agonist (TRI) and antagonist (BI) for forward reach. Baseline EMG (16-channel wireless system, Motion Lab Systems) values will be collected (2000 Hz) with the limb at rest in order to identify the ambient noise and isoelectric muscle activity signal level, then collected during reach-to-grasp movement. EMG data will be bandpass filtered (5 Hz – 1 kHz), demeaned, rectified and low-pass filtered with a fourth-order, zero-lag digital Butterworth filter (cutoff 20 Hz).

We will use Transcranial Magnetic Stimulation (TMS) to measure Neural Excitability: TMS analysis will be conducted at five time points (pre-intervention, end of weeks 1,2, and 3, and post-intervention)

Transcranial Magnetic Stimulation (TMS) is a means measuring the excitability of brain activity by generating a magnetic field that induces an electrical impulse into specific regions of the brain. The handheld TMS device that will be used in this study are two coils positioned side by side in a figure eight fashion. These coils, encased in plastic housing, produce a magnetic field that is only able to penetrate the outer layers of the cortex of the brain without causing pain or discomfort to the patient⁶⁹.

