Rationale: Very little is known about the neural and biomechanical mechanisms contributing to post-stroke UE motor impairment. Identification of the critical kinematic and neural aspects of reach contributing to changes in UE motor impairment occurring with therapy will permit refinement of existing and development of new interventions specifically targeted at improving these motor control process.

Approach: As described in the procedures above, we will collect kinematic and electromyographic (EMG) data to provide information about motor control strategies (kinematic) neural influences on motor output (EMG) responding to therapy.

Dependent Variable: The dependent variable will be change in UE motor impairment as measured by the percent change in the Rasch FMA-UE occurring from pre- to post-intervention as calculated above.

Independent Variables: We hypothesize that 3 independent variables will explain changes in UE motor impairment expected to occur with rehabilitation. These variables will be measured as the percent change in each variable occurring from pre- to post-intervention (post minus pre divided by pre). The variables were chosen because they are reasonable measures of "normal" movement based on the literature, motor control theory and clinical interpretation. Two kinematic variables (trunk movements, elbow extension range of motion) provide information about the strategy utilized to execute the movement. Trunk movement will be calculated as the cumulative distance a marker placed at T-10 travels during the reach. Voluntary elbow extension is calculated as difference between elbow joint angle at start and the joint angle at touch. One EMG variables (Biceps-Triceps co-

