If the subject agrees, the data collected and generated from this study will be shared and linked to RESTORE by the subject's registry ID. Sharing data from this study with the registry will allow for more targeted recruitment efforts in the future and allow researchers at MUSC to have a more complete registry with key stroke recovery elements including common data and physical function characteristics that are applicable to multiple studies.

Targeted/Planned Enrollment Table

Total Planned Enrollment - 130

TARGETED/PLANNED ENROLLMENT: Number of Subjects			
Ethnic Category	Sex/Gender		
	Females	Males	Total
Hispanic or Latino	3	4	7
Not Hispanic or Latino	48	75	123
Ethnic Category: Total of All Subjects*	130		
Racial Categories			
American Indian/Alaska Native	0	0	0
Asian	1	0	1
Native Hawaiian or Other Pacific Islander	0	0	0
Black or African American	16	25	41
White	34	54	88
Racial Categories: Total of All Subjects*	51	79	130

*The "Ethnic Category: Total of All Subjects" must be equal to the "Racial Categories: Total of All Subjects".

Inclusion criteria for the proposed study:

1. Experienced a stroke at least 3 months prior that has resulted in unilateral hemiparesis.
2. Passive range of motion in affected shoulder, elbow and wrist within functional limits;
3. 20-80 years of age.

Exclusion criteria for the proposed study:

1. Pain in the affected upper extremity that would limit participation in the study intervention.
2. Unable to understand 3-step directions;
3. Unable to attend the study-related treatment or evaluation sessions
4. Orthopedic condition in back or UE or impaired corrected vision that would alter kinematics of reaching.

We expect that our sample will have demographic characteristics similar to that of the general population in this region of South Carolina. These percentages, based on the 2010 census, reveal that the Charleston county area has a population that is 64% white, 30% African-American, 1% Asian, and 5% Hispanic and Latino and 39% female. There will be a total of 130 individuals with post-stroke UE hemiparesis enrolled in the overall study, and 10 subjects enrolled in this substudy..

No children will be included in this study.

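### Elbow extension is defined only at touch of the can, so an eligible severe patient who does not touch it at Pre has no value for the Aim 2 regression

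*Protocol*

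**What the plan says.** **Entry.** The main eligibility list (Protocol, section D) asks for "passive range of motion in affected shoulder, elbow and wrist within functional limits". The lists in Protection of Human Subjects and in the Appendix questionnaire also set passive range only. None sets a minimum active reach or a minimum FMA-UE score.

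**Severe level.** Table 4 places it below −0.22 logits with no floor. Table 1 describes these patients as "Fluctuating between unable and partial ability to perform movements requiring movement of arm away from body". (Section C gives a different cut: "the threshold marking the transition from severe to moderate = -0.12 logits". The two must be reconciled, but the point here holds under either.)

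**Test.** Procedure for Neuromechanical Evaluation reads: "subjects will perform 10 trials of reach-to-grasp (or touch) a soda can which will be placed at a location equal to 80% of". The percentage refers to the length of the arm, and the can stands in the midline. The trunk is free and the arm is not supported.

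**Variables.** Under Specific to Aim 2, "Voluntary elbow extension is calculated as difference between elbow joint angle at start and the joint angle at touch". Trunk movement is the distance that a T-10 marker travels during the reach. The co-contraction index is a ratio of EMG burst durations. Each predictor enters as (Post − Pre)/Pre. All are forced into two models, one per arm, each pooled over the three impairment levels.

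**Aim 3.** Growth classes come from repeated Rasch FMA-UE measures. Class membership is then related to pre-intervention elbow extension AROM, trunk movement and muscle co-activity.

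**Missing data.** The only rule is in the SAP, which covers Aim 1 only. It addresses missed visits and drop-out, with multiple imputation under missing at random.

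**The concern.** The elbow measure exists only if the hand reaches the can, and the plan admits and pools patients for whom this is in doubt. No rule covers a trial, or a patient, without a touch.

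The gap would not fall at random. It sits in one impairment level and, within that level, among the weakest patients. It also depends on response: someone who cannot touch the can at Pre but can at Post shows the kind of recovery that Aim 2 sets out to explain, yet has no Pre value from which to compute a change. If such patients are lost, the Aim 2 models describe severe patients who could already reach, while being presented as pooled over all levels.

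**Working it through.** **1. Planned numbers.** The Protocol's sample size reproduces. d = (2.30 − 1.42)/√[(1.00² + 0.45²)/2] = 0.88/0.775 = 1.13. A two-sided t-test at 0.05 with 90% power needs 17.3 to 17.5 per group, rounded up to 18. Six groups give 6 × 18 = 108. (The enrolment of 130 is 108 × 1.2 = 129.6; this does not bear on the point.) Each arm therefore has 3 × 18 = 54 planned completers, of whom 18 (33%) are severe. The Protocol gives no sample size, power or expected missingness for Aims 2 and 3.

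**2. Which inputs exist for a patient with no touch at Pre.**

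| Quantity | Needs touch? | Consequence |
|---|---|---|
| Elbow extension, Pre | Yes, by definition | No value |
| Elbow percent change (Aim 2) | Yes, divides by Pre | No value, even if the can is touched at Post |
| Trunk distance | Not stated; measured over the reach | End of the reach is unspecified |
| Co-contraction index | No | Available |
| Rasch FMA-UE and growth class | No | Available |
| Elbow predictor (Aim 3) | Only if the Aim 2 definition applies | Possibly no value |

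A forced-entry model fitted to complete cases drops a patient with one missing predictor.

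**3. Size.** The share f of severe patients with no touch at Pre is not in the documents, so it is an assumption. Lost per Aim 2 model = 18 × f.

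| f (assumed) | Lost | Share of 54 | Left |
|---|---|---|---|
| 10% | 1.8 | 3% | about 52 |
| 25% | 4.5 | 8% | about 49 |
| 50% | 9 | 17% | 45 |

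For illustration, take three predictors and an assumed R² of 0.20. The power of the overall F-test is 86% at n = 54, 84% at 52, 81% at 49 and 77% at 45. The loss of power is moderate; the selection matters more.

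**4. Is 10–50% reasonable?** Only indirect support is available. The two cuts in section C can be recovered from Table 2 with step thresholds of ±1.38: 1.26 − 1.38 = −0.12 and 1.06 + 1.38 = 2.44. The thresholds are back-solved and not stated in the Protocol. With them, the rating-scale model gives these probabilities of a rating of 0 (unable):

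| Person measure | Elbow extension (−0.64) | Shoulder flexion to 90° (−0.21) |
|---|---|---|
| −0.22 logits | 11% | 17% |
| −1 logit | 23% | 33% |
| −2 logits | 48% | 59% |

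These are FMA-UE items and not the can task, in which the trunk may help. They show that inability is expected within the level. They do not measure how often the can is missed.

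**5. Does a new end event alone repair Aim 2?** No. A patient who barely moves would have a Pre elbow change near zero, or negative if the elbow flexes. With Post = 20 degrees (illustrative), a Pre of 1 degree gives (20 − 1)/1 = +1900%, and a Pre of −1 degree gives (20 + 1)/(−1) = −2100%. A two-degree difference at Pre reverses the sign. Absolute change gives 19 and 21 degrees.

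**The case against.** The strongest reply is that few patients may be affected. Touch is enough, so grasp is not needed. The trunk is free, and section 2f says that trunk flexion takes the place of elbow extension in reaching. There are ten trials, so a patient who touches on some of them could still have a value. In the laboratory's earlier study (sections 3b and 3e), 52 of 55 completed testing and the severe category yielded elbow AROM values. The severe example patient had reach data despite "utilizing approximately 20 degrees of shoulder flexion and virtually no elbow extension during the task". Section C also lists elbow extension and shoulder flexion among movements that severe patients can partly perform. Finally, the Protocol cites published test procedures, which may contain a trial-end rule that cannot be seen here.

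This stands as a reason to expect a small number, and it makes the low end of the range (2 of 54) credible. It does not close the gap. One severe patient with data shows that the task is possible for some, and the text does not say whether that patient touched the can. The Protocol states no rule for trials without touch, nor how touched and untouched trials combine.

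A reader might also infer more than the documents support:

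- **That the plan excludes these patients.** It does not say so. Exclusion is what complete-case fitting does by default; handling in Aims 2 and 3 is simply unspecified. The SAP's imputation could be extended to keep them, but missing at random is doubtful when a value is absent because the patient could not reach.
- **That trunk distance is undefined too.** It is not tied to touch; its end point is only unstated.
- **That Aim 3 as a whole describes only patients who could reach.** The growth classes rest on FMA-UE and keep every patient. Only the class-predictor step is exposed, and the Protocol does not say that elbow extension AROM there is the at-touch measure.

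**Conclusion.** The concern holds for the elbow-extension variable. Its definition does not cover patients whom the plan admits and says it pools, and the resulting gap is related to severity and to response. By default the loss falls on the Aim 2 regressions, and on the Aim 3 class-predictor step if the same definition is used there.

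The size is about 2–9 of 54 planned completers per Aim 2 model (3–17%), all from the severe level. This rests on an assumed 10–50% unable to touch at Pre, on 18 severe completers per arm as the sample size implies, and on complete-case fitting. The true share is unknown and may be lower. Aim 1, the powered comparison, is not affected. The change is worth making before the kinematic data are processed, because the rule then cannot depend on who turned out to improve.

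**What to change.** In the Protocol, Specific to Aim 2, Independent Variables:

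1. Define the end event as touch or, if the can is not touched, the point of greatest wrist-marker advance toward the can. Use it for elbow extension, and state it as the end of the reach for trunk distance, at Pre, Mid and Post.
2. Record touch (yes/no) for each trial and report no-touch counts by arm and visit.
3. In Aim 2, enter elbow extension as absolute change in degrees (Post minus Pre) in place of (Post − Pre)/Pre.
4. Under Aim 3, say whether baseline elbow extension AROM is this same variable.

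**Cost.** A few sentences and a change to the processing code. The marker data are already recorded, so no test or treatment procedure changes. The Aim 2 elbow coefficient will be per degree and not per percent. Values from touched and untouched trials are not fully equivalent; the touch flag lets the analyst check this, for example by refitting without the untouched trials.

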contraction index) provide information regarding neural influences on motor output. The mean amplitude obtained during 5 sec. resting EMG activity will be used as baseline EMG values. For each trial, "time-to-EMG" is calculated as the difference between muscle onset and movement onset. Muscle onset is defined as a rise in EMG exceeding 4 standard deviations above resting EMG. Muscle offset is defined as a decrease in EMG below this value. Movement onset is defined as the time-point when velocity of the wrist marker exceeded 5% peak velocity. Positive time-to-EMG values indicate anticipatory muscle activation (occurred prior to movement onset); negative time-to-EMG values indicate delayed muscle activation (occurred after movement onset). The EMG activity occurring between onset and offset is defined as burst duration. A co-contraction index variable will be defined as Biceps Burst Duration divided by Triceps Burst Duration so that a value equal to 1 reflects simultaneous activity of the agonist and antagonist.

Data analysis: Two multiple regression models will examine the relationships between the dependent and independent variables. One regression model will include variables from all patients involved in targeted-therapy (i.e., pooled data from across UE impairment levels). The second model will include variables from all patients involved in non-targeted therapy.

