Data analysis: Data from participants in targeted-rehabilitation protocols will be pooled and analyzed. Three models will be tested in accordance with our a-priori hypothesis that each level of impairment (mild, moderate, severe) should show distinct patterns of recovery, i.e., we expect 3 classes of recovery. Specifically, we will test whether there is one overall pattern of recovery that describes the entire sample (1-class), whether there are two patterns of recovery within the sample (2-class) or whether there are three patterns of recovery in the sample (3-class). The models are not nested (a 1-class model is not a subset of the 2-class model) because different individuals make up each class. Therefore the chi-square model comparison test is not appropriate. Instead, we will define the best fitting model as the one having the lowest Bayesian Information Criteria (BIC) and an entropy value closest to 1.0.

To determine the best predictors of recovery patterns we will use logistic regression to relate recovery pattern (growth class membership) to kinematic and EMG variables hypothesized to be important predictors of recovery. The predictors hypothesized to be important are baseline elbow extension AROM, amount of trunk movement, and muscle co-activity. The predictor variables entered into analysis will be collected pre-intervention. Predictors will be examined to determine those which significantly discriminate class membership. Because the predictors are allowed to vary across classes, the analysis will provide a means of examining whether predictors of one trajectory differ across each trajectory. For example, loss of elbow extension AROM may be the most significant predictor of membership in one class, while inability to activate agonist muscles may be the most significant predictor of another recovery pattern.

Methods specific to the SUBSTUDY

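### The biceps-triceps co-contraction index compares burst lengths, not timing, so it does not measure co-activity in Aim 2, nor in Aim 3 if the same index is used there

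*Protocol*

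**What the plan says.** The definition is in the Protocol, section D, Specific to Aim 2, Independent Variables:

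- Each muscle's burst is timed separately, with onset and offset set by a threshold 4 SD above resting EMG: "The EMG activity occurring between onset and offset is defined as burst duration".
- The index is the ratio of the two: "A co-contraction index variable will be defined as Biceps Burst Duration divided by Triceps Burst Duration".
- The Protocol explains this choice by its reading of one particular value. The ratio is formed, it says, "so that a value equal to 1 reflects simultaneous activity of the agonist and antagonist".
- Onset timing is computed as time-to-EMG, which "is calculated as the difference between muscle onset and movement onset". It does not enter the index.
- "We hypothesize that 3 independent variables will explain changes in UE motor impairment", and the index is the only EMG variable among them. Each enters as "percent change in each variable occurring from pre- to post-intervention (post minus pre divided by pre"). All are forced into both Aim 2 regression models.

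For Aim 3 (Data analysis), "The predictors hypothesized to be important are baseline elbow extension AROM, amount of trunk movement, and muscle co-activity", all measured before the intervention. The Aim 3 text does not name the index, but the Protocol defines no other measure of co-activity. Background section 2f expects recovery to bring less co-activity. The Protocol does not say whether a rise or a fall in the index is improvement. The SAP covers Aim 1 only and does not alter any of this.

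**The concern.** Co-activity means that biceps and triceps are on at the same time. Two burst lengths cannot show this, because they do not say when either burst occurred. The value 1, which the Protocol reads as simultaneous activity, only means that the bursts last equally long.

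The percent-change scale raises a second question. If 1 is the point of greatest co-activity, patients can approach it from above or below, and the same physiological change then takes opposite signs. A third is that the ratio has no value when the denominator muscle shows no burst.

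At stake is what the EMG coefficient in Aim 2, and the co-activity coefficient in Aim 3, can be said to show. A null or significant result could not be read as evidence about co-activity. Aim 1, the treatment comparison, does not use the variable.

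**Working it through.** The plan gives no figure that depends on the index, so there is nothing to reproduce. The check tests the plan's own statement about the value 1.

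**1. Does an index of 1 imply simultaneous activity?**

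Index = biceps burst length / triceps burst length. Overlap share = time both muscles are on / time either is on. The burst times are illustrative.

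| Biceps (ms) | Triceps (ms) | Index | Overlap share |
|---|---|---|---|
| 0-300 | 500-800 | 300/300 = 1.0 | 0/600 = 0% |
| 0-600 | 0-600 | 600/600 = 1.0 | 600/600 = 100% |
| 0-400 | 200-600 | 400/400 = 1.0 | 200/600 = 33% |
| 0-800 | 0-400 | 800/400 = 2.0 | 400/800 = 50% |

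An index of 1 fits any overlap from none to complete. In the last row the biceps is on for the whole triceps burst, yet the index is 2. This step needs no assumption about the patients.

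**2. Does the percent change have a fixed direction (Aim 2)?**

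Take the Protocol's reading that 1 means simultaneous, and apply (post - pre)/pre:

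- 2 to 1: (1 - 2)/2 = -50%, toward 1.
- 0.5 to 1: (1 - 0.5)/0.5 = +100%, also toward 1.
- 0.5 to 0.75 and 2 to 3: both +50%, one toward 1 and one away.
- 0.5 to 2: +300%, with no change in distance from 1 on the log scale.

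The recovery expected in section 2f would be movement away from 1. It splits the same way: 1 to 0.5 is -50% and 1 to 2 is +100%.

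**3. How much would this cost?**

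The documents give no index values, so the distribution is assumed: log(index) normal, SD 0.3 or 0.5 at both visits, pre-post correlation 0.6. Movement toward 1 is the fall in |log(index)|. R² is the share of that movement explained by percent change.

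| Median index | Patients below 1 at Pre (SD 0.3 / 0.5) | R² (SD 0.3 / 0.5) |
|---|---|---|
| 1.0 | 50% / 50% | below 0.001 / below 0.001 |
| about 1.35 | 16% / 27% | 0.59 / 0.27 |
| about 2.0 | 1% / 8% | 0.95 / 0.74 |
| about 0.5 | 99% / 92% | 0.95 / 0.73, sign reversed |

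The loss runs from near total, when patients straddle 1, to small, when nearly all lie on one side.

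**4. Do the planned remedies help?**

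The Aim 2 Data analysis text allows a quadratic term and a log transform. The quadratic term acts on percent change, not on distance from 1. It adds nothing at a median of 1.0 and at most 0.07 to R² elsewhere in the table. The logarithm does not exist for a negative percent change.

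**5. When is the index undefined?**

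When the triceps does not cross the 4-SD threshold in a trial, there is no triceps burst to divide by. No rule covers this. The Aim 3 text itself offers failure to activate agonist muscles as an example of a predictor, and the Procedure for Neuromechanical Evaluation names the triceps as agonist.

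**The case against.** Three defences deserve weight.

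- **The ratio may be meant one way only**, with a lower value meaning less antagonist activity relative to the agonist. That removes the sign problem. But then 1 has no special meaning, and the variable is relative burst length, not the co-activity named in the hypotheses.
- **The ratio may work as a proxy if both bursts start almost together.** With assumed burst lengths (median 400 ms, log SD 0.4), closeness to 1 correlates 0.86 with overlap when the onset lag has SD 50 ms, 0.47 at 150 ms and 0.22 at 300 ms. The raw ratio that the plan uses correlates only -0.27, -0.15 and -0.07. Any proxy value depends on a lag that the index ignores.
- **The mechanism work is presented as exploratory**, and the plan expects non-linear relations. This limits the importance of the point but does not repair the measure.

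A reader might also draw stronger conclusions that the documents do not support:

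- **That signs will conflict in the data.** This needs patients on both sides of 1, and no index values are given.
- **That the percent-change problem reaches Aim 3.** Aim 3 uses pre-intervention levels. Only the construct problem carries over, together with a level that is two-sided around 1, and only if the unnamed co-activity variable is this index.
- **That severe patients will be lost selectively.** Section 3d describes severe patients as partly able to extend the elbow, and each session has 10 trials, so one silent trial need not lose a patient. It could happen more often in severe patients, but no rate is given.

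**Conclusion.** The point holds. By arithmetic on the Protocol's own definitions, an index of 1 does not establish simultaneous activity, and nothing else in the Protocol or SAP corrects this. The only EMG predictor in Aim 2 does not measure what it is named for. The same is true of one of the three Aim 3 predictors if it is the same index, which is an inference from the absence of any other definition.

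The sign problem is confined to Aim 2 and is conditional. Under the assumed distributions, percent change captures from about 0% to about 95% of the movement toward 1, depending on where patients lie. An undefined index for trials with a silent triceps is a real gap of unknown frequency.

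It would go too far to say that Aims 2 and 3 fail as a whole. The two kinematic predictors stand, and Aim 1 is not affected. The change should be made before analysis, but it does not bear on the trial's main comparison.

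**What to change.** Before analysis, by documented amendment:

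1. Define co-contraction, from the onset and offset times that the plan already extracts, as the time both muscles are active divided by the time either is active. State that a lower value means less co-activity.
2. Enter the absolute Pre-to-Post change in Aim 2 and the Pre value in Aim 3, and say in the Aim 3 text that this is the variable meant.
3. Do not score a trial as 0 when no triceps burst, or no burst in either muscle, is detected. A silent triceps with an active biceps would otherwise receive the same value as clean triceps-only activation, and so count failed agonist activation as the best result. With neither muscle active the measure is 0/0. Flag these trials and report their number by impairment level.

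The cost is a definition, an amendment and a small script change, with no new measurement. The downside is that overlap does not show which muscle is prolonged: biceps 0-600 ms with triceps 0-300 ms, and the reverse, both score 0.5, where the ratio gives 2.0 and 0.5. The ratio can therefore be kept as a descriptive variable under the name relative burst duration.
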